10.9. Appendix 9: Thrombotic Events to be Reported as AESIs

At the time of protocol writing, the list of thrombotic events to be reported to the sponsor as AESIs is provided below. Further guidance may become available on thrombotic events of interest.

- MedDRA PTs for large vessel thrombosis and embolism:
 - Aortic embolus, aortic thrombosis, aseptic cavernous sinus thrombosis, brain stem embolism, brain stem thrombosis, carotid arterial embolus, carotid artery thrombosis, cavernous sinus thrombosis, cerebral artery thrombosis, cerebral venous sinus thrombosis, cerebral venous thrombosis, superior sagittal sinus thrombosis, transverse sinus thrombosis, mesenteric artery embolism, mesenteric artery thrombosis, mesenteric vein thrombosis, splenic artery thrombosis, splenic embolism, splenic thrombosis, thrombosis mesenteric vessel, visceral venous thrombosis, hepatic artery embolism, hepatic artery thrombosis, hepatic vein embolism, hepatic vein thrombosis, portal vein embolism, portal vein thrombosis, portosplenomesenteric venous thrombosis, splenic vein thrombosis, spontaneous heparin-induced thrombocytopenia syndrome, femoral artery embolism, iliac artery embolism, jugular vein embolism, jugular vein thrombosis, subclavian artery embolism, subclavian vein thrombosis, obstetrical pulmonary embolism, pulmonary artery thrombosis, pulmonary thrombosis, pulmonary venous thrombosis, renal artery thrombosis, renal embolism, renal vein embolism, renal vein thrombosis, brachiocephalic vein thrombosis, vena cava embolism, vena cava thrombosis, truncus coeliacus thrombosis
- MedDRA PTs for more common thrombotic events:
 - Axillary vein thrombosis, deep vein thrombosis, pulmonary embolism, MedDRA PTs for acute myocardial infarction*, MedDRA PTs for stroke*

Source: Shimabukuro T. CDC COVID-19 Vaccine Task Force. Thrombosis with thrombocytopenia syndrome (TTS) following Janssen COVID-19 vaccine. Advisory Committee on Immunization Practices (ACIP). April 23, 2021. <https://www.cdc.gov/vaccines/acip/meetings/slides-2021-04-23.html>.

*Vaccine Adverse Event Reporting System (VAERS) Standard Operating Procedures for COVID-19 (as of 29 January 2021) <https://www.cdc.gov/vaccinesafety/pdf/VAERS-v2-SOP.pdf>

10.10. Appendix 10: Protocol Amendment History

This is an original protocol.

## VERSION HISTORY

**Table 1 – SAP Version History Summary**

SAP Version	Approval Date	Change	Rationale
0.1	Not Applicable	Not Applicable	Initial draft release
0.2	Not Applicable	First review and comments from COV3005 Team	Initial draft release
0.3	Not Applicable	Responses to first review, HA FDA protocol review integration and second review	Initial draft release
0.4	Not Applicable	Responses to second review	Initial draft release
0.5	Not Applicable	Responses to third review	Initial draft release
0.6	Not Applicable		Protocol Amendment 1
0.7	Not Applicable		Clarification for populations and subgroup analyses

## 1. INTRODUCTION

This Statistical Analysis Plan (SAP) contains information needed to perform the complete safety and immunogenicity analysis of the VAC131518COV3005 trial. It describes more technically and with more details the pre-planned analysis for the Primary Analysis and Final Analysis found in the Section 9.4 of the clinical trial protocol (CTP). A Data Presentation Specification Document (DPS) will be available to further detail the statistical outputs that will be generated.

### 1.1. Objectives and Endpoints

Objectives	Endpoints
Primary To demonstrate the NI of the humoral immune response of the 4 influenza vaccine strains after concomitant administration of the Ad26.COV2.S vaccine and a seasonal quadrivalent standard-dose influenza vaccine versus the administration of a seasonal quadrivalent standard-dose influenza vaccine administered alone.	
 
Antibody hemagglutination inhibition (HI) titers as measured by hemagglutinin inhibition (HAI) assay titers (geometric mean titers [GMTs]) against each of the 4 influenza vaccine strains, 28 days after the administration of a seasonal quadrivalent standard-dose influenza vaccine.
 
 
Success criteria for NI
 
 
the upper bound of the 2-sided 95% confidence interval (CI) for the geometric mean titer (GMT) ratio (Control group/co-administration [CoAd] group) lies below 1.5
 

To demonstrate the NI of the binding antibody response after concomitant administration of Ad26.COV2.S vaccine and a seasonal quadrivalent standard-dose influenza vaccine versus the administration of Ad26.COV2.S vaccine administered alone.	
 
Antibody titers as measured by S enzyme-linked immunosorbent assay (S-ELISA) titers (GMC), 28 days after administration of Ad26.COV2.S vaccine.
 
 
Success criteria for NI

Objectives	Endpoints
	
 
the upper bound of the 2-sided 95% confident interval (CI) for the GMC ratio (Control group/CoAd group) lies below 1.5
 

Secondary	
To assess the safety and reactogenicity of a single dose of Ad26.COV2.S vaccine when administered separately or concomitantly with a seasonal quadrivalent high-dose influenza vaccine in participants aged 65 years and older.	
 
Solicited local (injection site) and systemic AEs for 7 days after each vaccination.
 
Unsolicited AEs for 28 days after each vaccination.
 
SAEs, MAAEs, and AESIs throughout the study.
 
AEs leading to withdrawal from the study throughout the study.
 

To assess the safety and reactogenicity of a single dose of Ad26.COV2.S vaccine when administered separately or concomitantly with a seasonal quadrivalent standard-dose influenza vaccine in participants aged 18 years and older.	
 
Solicited local (injection site) and systemic AEs for 7 days after each vaccination.
 
Unsolicited AEs for 28 days after each vaccination.
 
SAEs, MAAEs, and AESIs throughout the study.
 
AEs leading to withdrawal from the study throughout the study.
 

To assess the humoral immune response against each of the 4 influenza vaccine strains after concomitant administration of the Ad26.COV2.S vaccine and a seasonal quadrivalent high-dose influenza vaccine versus the administration of a seasonal quadrivalent high-dose influenza vaccine administered alone.	
 
Antibody HI titers as measured by HAI assay titers (GMTs) against each of the 4 influenza vaccine strains, 28 days after the administration of a seasonal quadrivalent high-dose influenza vaccine.
 

To assess the humoral immune response of Ad26.COV2.S vaccine and a seasonal quadrivalent high-dose influenza vaccine versus the administration of a seasonal quadrivalent high-dose influenza vaccine administered alone.	
 
Antibody titers as measured by S enzymelinked immunosorbent assay (S-ELISA) titers (GMC), 28 days after administration of Ad26.COV2.S vaccine.
 

To assess the humoral response to SARS-CoV-2 after the concomitant administration of Ad26.COV2.S vaccine and a seasonal quadrivalent high-dose influenza vaccine versus the administration of Ad26.COV2.S vaccine alone in COVID-19 vaccine-naïve individuals .	
 
Antibody titers as measured by S enzymelinked immunosorbent assay (S-ELISA) titers (GMC), 28 days after administration of Ad26.COV2.S vaccine.
 

To assess the humoral response to SARS-CoV-2 after the concomitant administration of Ad26.COV2.S vaccine and a seasonal quadrivalent standard-dose influenza vaccine versus the administration of Ad26.COV2.S vaccine alone in COVID-19 vaccine-naïve individuals .	
 
Antibody titers as measured by S enzymelinked immunosorbent assay (S-ELISA) titers (GMC), 28 days after administration of Ad26.COV2.S vaccine.
 

To compare seroconversion rates against the 4 influenza vaccine strains after the concomitant	
 
Seroconversion is defined for each of the 4 influenza vaccine strains at 28 days after the
 

Objectives	Endpoints
administration of Ad26.COV2.S vaccine and a seasonal quadrivalent ( high-dose and standard-dose ) influenza vaccine versus a vaccination of a seasonal quadrivalent ( high-dose and standard-dose ) influenza vaccine administered alone.	
administration of a seasonal quadrivalent (high-dose and standard-dose) influenza vaccine:
 
 
- HI titer <math>\geq 1:40</math> in participants with a pre-vaccination HI titer of <math>< 1:10</math>, or
 
- a <math>\geq 4</math>-fold HI titer increase in participants with a pre-vaccination HI titer of <math>\geq 1:10</math>.
 

To assess seroprotection rates against the 4 influenza vaccine strains after the concomitant administration of Ad26.COV2.S vaccine and a seasonal quadrivalent ( high-dose and standard-dose ) influenza vaccine versus a vaccination of a seasonal quadrivalent ( high-dose and standard-dose ) influenza vaccine administered alone.	
 
• Seroprotection is defined for each of the 4 influenza vaccine strains as HI titer <math>\geq 1:40</math> at 28 days after the administration of a seasonal quadrivalent (high-dose and standard-dose) influenza vaccine.
 

Exploratory	
To evaluate the durability of influenza-specific humoral immune responses after concomitant administration of the vaccines versus the influenza vaccine alone.	
 
• GMT: Geometric mean of HI antibodies at Day 181.
 
• Percentages of participants with HI titers <math>\geq 1:40</math> on Day 181.
 

To evaluate the durability of SARS-CoV-2 specific humoral immune responses after concomitant administration of the vaccines versus the SARS-CoV-2 vaccine alone.	
 
• Antibody GMC by S-ELISA at Day 181 after the administration of Ad26.COV2.S vaccine.
 

To assess the magnitude and durability of humoral immune responses specific to influenza.	
 
• Serological responses to vaccination as measured by HAI at Day 181 after the administration of influenza vaccine.
 

## 1.2. Study Design

This is a randomized, double-blind, parallel, multicenter, interventional study in healthy (including stable comorbidities) adults  $\geq 18$  years of age. In this study, the safety, reactogenicity, and immunogenicity of Ad26.COV2.S co-administered with a seasonal influenza vaccine will be evaluated.

Participants will be randomized in parallel in this study. Participants aged  $\geq 65$  will be randomized in a 1:1:1:1 ratio to 1 of 4 groups. Participants aged  $\leq 64$  will be randomized in a 1:1 ratio to 1 of 2 groups (Group 1 or Group 2). Efforts will be made to ensure good representation in terms of race, gender, and ethnicity.

Participants will receive Ad26.COV2.S and a seasonal quadrivalent (*standard-dose* or *high-dose*) influenza vaccine either concomitantly on Day 1 and placebo on Day 29 (co-administration groups 1 and 3) or a seasonal quadrivalent (*standard-dose* or *high-dose*) influenza vaccine and placebo on Day 1 and Ad26.COV2.S on Day 29 (control groups 2 and 4) (see table 2 below).

**Table 1: Overview of the Groups and Vaccinations**

Group	Day 1	Day 29
1 (CoAd group)	Ad26.COV2.S + Q SD influenza vaccine	Placebo
2 (Control group)	Placebo + Q SD influenza vaccine	Ad26.COV2.S
3 (CoAd group)	Ad26.COV2.S + Q HD influenza vaccine	Placebo
4 (Control group)	Placebo + Q HD influenza vaccine	Ad26.COV2.S

CoAd = coadministration; HD = high-dose; Q = quadrivalent; SD = standard-dose.

The seasonal quadrivalent *standard-dose* influenza vaccine (Groups 1 and 2) can be administered to all participants. Age is included as stratification factor for Groups 1 and 2 ( $\geq 18$  to  $\leq 64$  years of age versus  $\geq 65$  years of age). The seasonal quadrivalent *high-dose* influenza vaccine (Groups 3 and 4) will only be administered to participants  $\geq 65$  years of age.

The previous SARS-CoV-2 vaccination history (Vaxzevria [AstraZeneca], Comirnaty [Pfizer-BioNTech], SpikeVax [Moderna], and Ad26.COV2-S [Janssen]) will be used as second stratification factor during the randomization process. These stratification levels will ensure well-distributed proportional representation of each previous vaccines within each of the 4 study groups.

Enrollment will be monitored weekly for age group and previous vaccination history to ensure sites are enrolling a diverse population of participants and similar proportions of previous vaccines within each group.

Participants can either have received a complete primary vaccination with an authorized/licensed COVID-19 vaccine (completed  $\geq 6$  months prior to first study vaccination) or be COVID-19 vaccine-naïve. The type of primary vaccination will be documented and accounted for according to interactive web response system (IWRS) procedures.

The study duration from screening until the last follow-up visit will be approximately 7-8 months. The study comprises screening on Day -28 to 1, vaccination visits on Days 1 and 29 with a 28-day follow-up period after each vaccination. AEs leading to withdrawal, MAAEs, SAEs, and AESIs will be collected throughout the study.

## **2. STATISTICAL HYPOTHESES**

No formal statistical testing of safety data is planned. Safety data will be analyzed descriptively by vaccine group.

The study is successful if the below objectives are demonstrated:

- NI of the humoral immune response as measured by the HI assay after concomitant administration of Ad26.COV2.S vaccine and a seasonal *standard-dose* influenza vaccine versus the administration of a seasonal quadrivalent *standard-dose* influenza vaccine alone, 28 days after the administration of a seasonal influenza vaccine.

AND

- NI of the concomitant administration of Ad26.COV2.S vaccine and a seasonal quadrivalent *standard-dose* influenza vaccine versus the administration of Ad26.COV2.S vaccine alone, 28 days after the administration of Ad26.COV2.S vaccine, in terms of humoral immune response (ELISA)

Therefore, the following confidence intervals (CIs) will be calculated:

- The 2-sided 95% CIs for the difference in log-transformed HI antibody titers against each of the 4 seasonal influenza vaccine strains at 28 days after the administration of the quadrivalent seasonal influenza vaccine between the Control and the CoAd group, and
- The 2-sided 95% CIs for the difference in log-transformed ELISA titers at 28 days after the administration of Ad26.COV2.S vaccine between the Control and the CoAd group

Only if the upper bound of the 2-sided 95% CI for the GMT ratio (Control group/CoAd group) of the HI antibody titer for each of the 4 vaccine strains and for S-ELISA lies below 1.5, NI of coadministration versus separate administration will be concluded for both vaccines (seasonal

influenza vaccine and Ad26.COV2.S vaccine). If 1 or more confidence limits for the GMT ratio exceed 1.5, NI cannot be concluded.

The primary analysis will be performed when all participants have completed the 28 days after the second study vaccination visit or discontinued earlier. No interim analyses will be performed.

### 3. SAMPLE SIZE DETERMINATION

Sample size calculations are performed under the following assumptions:

- no effect of coadministration of Ad26.COV2.S vaccine and seasonal influenza vaccine on the immune response against influenza as measured by HI antibody titers against the 4 influenza vaccine strains at 28 days after the administration of seasonal influenza vaccine
- the use of Afluria Quadrivalent for *standard-dose* (adults  $\geq 18$  to  $<64$  years of age and older adults  $\geq 65$  years of age)
- a standard deviation of between 0.53 for the *standard-dose* at the  $\log_{10}$  scale for HI antibody titers against the 4 influenza vaccine strains at 28 days after the administration of seasonal influenza vaccine (with or without Ad26.COV2.S)
- no effect of coadministration of Ad26.COV2.S vaccine and seasonal influenza vaccine on the immune response against SARS-CoV-2 as measured by S-ELISA at 28 days after the administration of Ad26.COV2.S vaccine
- a standard deviation of 0.50 at the  $\log_{10}$  scale for S-ELISA at 28 days after the administration of Ad26.COV2.S vaccine (with or without seasonal influenza vaccine)
- Log transformed ( $\log_{10}$  scale) immune response data are normally distributed
- a non-inferiority margin of 1.5
- 2-sided  $\alpha$  of 5%

A total of approximately 305 (*standard-dose*) participants per group are needed to have 97.45% power to show non-inferiority in HI antibody titers for each influenza vaccine strain.

The sample size accounts for exclusions from the per protocol set, drop-outs and missing samples resulting in a total sample size up to approximately 610 participants who have completed a primary COVID-19 vaccine series. The N margin was  $\sim 10\%$  ( $\sim 30$  per group).

With this sample size, the overall power to show NI in HI antibody titers against each of the 4 influenza vaccine strains at 28 days after the administration of seasonal influenza vaccine as well as NI in S-ELISA at 28 days after the administration of Ad26.COV2.S vaccine is at least 90%.

### 4. POPULATIONS (ANALYSIS SETS) FOR ANALYSIS

Analysis Sets	Description
All screened participants (ALL)	The “all screened participants” set includes all participants that were screened, regardless of whether they were enrolled and/or randomized.

Analysis Sets	Description
All randomized participants (ALL RANDOMIZED)	The “all randomized participants” set includes all participants that were randomized to one of the treatment groups.
Full Analysis Set (FAS)	The full analysis set (FAS) includes all participants with a vaccine administration documented.
Per-protocol Influenza Immunogenicity (PPII) Set	
Per Protocol Influenza Immunogenicity (PPII) Set: All randomized participants who received Ad26.COV2.S vaccine in combination with a seasonal influenza vaccine for the coadministration group and those who received a seasonal influenza vaccine alone for the control group, for whom immunogenicity data are available for at least one of the influenza strains in the vaccine.
 
PPII set will include participants who have received a complete primary vaccination with an authorized/licensed COVID-19 vaccine as well as COVID-19 vaccine-naïve participants.
 
Samples taken after (but not before) a participant experienced a confirmed major protocol deviation expected to impact the immunogenicity outcomes will be excluded from the PPII analysis.
 
The primary analysis set for analyses related to influenza immunogenicity is the PPII Set. As a sensitivity analysis, key tables may also be based on the FAS.

Per-Protocol SARS-CoV-2 Immunogenicity (PPSI) Set	
The per protocol SARS-CoV-2 Immunogenicity Set (PPSI) will include all randomized participants who received Ad26.COV2.S vaccine in combination with seasonal influenza vaccine for the co-administration group and Ad26.COV2.S vaccine alone for the control group, and for whom immunogenicity data are available.
 
PPSI set will be restricted to participants who have received a complete primary vaccination with an authorized/licensed COVID-19 vaccine.
 
N seronegative participants at day 1 that became N serology positive during the study will be excluded for analyses of future timepoints.
 
Participants with positive molecular test for SARS-CoV-2 will also be excluded from future timepoints.
 
Samples taken after a participant meets the criteria for a major protocol deviation expected to impact the immunogenicity outcomes will be excluded from the PPSI analysis.

Analysis Sets	Description
Per-Protocol SARS-CoV-2 Immunogenicity (PPSI2) Set including vaccine-naïve participants.	
The primary analysis set for analyses related to SARS-CoV-2 immunogenicity is the PPSI Set. As a sensitivity analysis, key tables may also be presented as part of the FAS.

Safety	
The per protocol SARS-CoV-2 Immunogenicity Set (PPSI2) will include all randomized participants (vaccine-naïve and previously vaccinated) who received Ad26.COV2.S vaccine in combination with seasonal influenza vaccine for the co-administration group and Ad26.COV2.S vaccine alone for the control group, and for whom immunogenicity data are available.
 
N seronegative participants at day 1 that became N serology positive during the study will be excluded for analyses of future timepoints.
 
Participants with positive molecular test for SARS-CoV-2 will also be excluded from future timepoints.
 
Samples taken after a participant meets the criteria for a major protocol deviation expected to impact the immunogenicity outcomes will be excluded from the PPSI2 analysis.

Note: Participants who have a self-confirmed history of SARS-CoV-2 infection at screening or positive N-serology at Day 1 will be included in the analysis.

## 5. STATISTICAL ANALYSES

### 5.1. General Considerations

The primary analysis will be performed when all participants have completed the 28 days after the second study vaccination visit or discontinued earlier. No interim analyses will be performed.

#### 5.1.1. Visit Windows

For the immunogenicity analysis, assessments will be allocated to an analysis visit based on the planned visit as captured in the CRF. Visits that are out of the protocol-defined visit windows (see Table 2) will not be included in the per-protocol immunogenicity analysis. However, they may be included in sensitivity analyses.

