1.3. Schedule of Activities

1.3.1. All Participants

Phase	Screening ^a	Treatment Phase ^b					Follow Up ^b		Early termination ^{b,d}
		1	2	Phone Call ^c	3	Phone Call ^c	4	Phone Call	
Clinic Visit #	1			Vac 1	Vac 2	Vac 2	Post Vac 2	Post Vac 2	Exit ^d
Visit Timing		Vac 1 + 7 d		+ 7 d	+ 7 d	+ 28 d	+ 90 d	+ 180 d	
Visit Day/Week	-28 to 1	Day 1	Day 8	Day 29	Day 36	Day 57	Week 16 (3 mo post Vac 2)	Week 28 (6 mo post Vac 2)	
Visit Window		N/A	±3 d	-3/+7 d	±3 d	-3/+7 d	±7 d	±7 d	
Visit Type	Screening	Vaccination, Immunogenicity and Safety	Safety	Vaccination, Immunogenicity and Safety	Safety	Immunogenicity and Safety	Safety	Immunogenicity and Safety	End of Study
Written informed consent ^e	●								
Inclusion/exclusion criteria	●	● ¹							
Demographics	●								
Medical history/prestudy medications	●								
History of SARS CoV 2 vaccination ^f	●								
Physical examinations	●								
Vital signs ^h including body temperature	●	● ²		● ²		●		●	●
Randomization		● ¹							
Pre vaccination check ⁱ		● ¹		● ¹					
Urine pregnancy test ^j	●	● ¹		● ¹					
Humoral Immunity (serum), blood draw, 15 mL		● ¹		● ¹		●		●	● ³
Laboratory assessments: blood draw (whole blood / serum/ plasma), approx. 15 mL ^k		● ¹		● ¹					
Vaccination		●		●					
15 minutes post vaccination observation ^l		●		●					
Solicited AE recording		From Vac 1 +7 d		From Vac 2 +7 d					● ⁴

Phase	Screening ^a	Treatment Phase ^b					Follow Up ^b		Early termination ^{b,d}
Clinic Visit #	1	2	Phone Call ^c	3	Phone Call ^c	4	Phone Call	5	Exit ^d
Visit Timing		Vac 1	Vac 1 + 7 d	Vac 2	Vac 2 + 7 d	Post Vac 2 + 28 d	Post Vac 2 + 90 d	Post Vac 2 + 180 d	
Visit Day/Week	-28 to 1	Day 1	Day 8	Day 29	Day 36	Day 57	Week 16 (3 mo post Vac 2)	Week 28 (6 mo post Vac 2)	
Visit Window		N/A	±3 d	-3/+7 d	±3 d	-3/+7 d	±7 d	±7 d	
Visit Type	Screening	Vaccination, Immunogenicity and Safety	Safety	Vaccination, Immunogenicity and Safety	Safety	Immunogenicity and Safety	Safety	Immunogenicity and Safety	End of Study
Unsolicited AE recording ^m		----- From Vac 1 through Vac 2 +28 d -----							● ⁵
SAE ⁿ and AESI ^o recording		----- Throughout the study -----							●
AEs leading to withdrawal		----- Throughout the study -----							●
COVID 19 recording ^p		----- Throughout the study -----							●
MAAE recording ^q		----- Throughout the study -----							●
Concomitant medications ^r		----- Throughout the study -----							●
Participant diary distribution ^s		●							
Investigator's assessment of reactogenicity ^t			●		●				

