Approx. blood draw per day, mL:		30		30		15		15	● ³ 15
Approx. cumulative blood draw, mL:		30		60		75		90	

●¹ pre vaccination; ●² pre and post vaccination; ●³ blood samples for immunogenicity will only be taken if the early exit visit is at least 10 days after the previous immunogenicity blood draw; ●⁴ if within 7 days of the vaccination; ●⁵ if within 28 days of the vaccination.

The phone call or these visits (including their window) are to be scheduled relative to the actual day of the previous vaccination, indicated as Visit Timing days/weeks post vaccination.

- Screening can be performed within 28 days prior to the first study vaccination or on the day of vaccination. If screening is performed on the day of vaccination, Visit 1 and Visit 2 will coincide on Day 1. Screening must be completed, and all eligibility criteria must be fulfilled prior to randomization and vaccination.
- If a participant shows COVID 19 like symptoms, the participant should contact the site for guidance and must follow their local country and site level recommendations for COVID 19.
- The site will contact the participant 7 days post vaccination 1, and 7 days post vaccination 2 to enquire about compliance and severe symptoms reported on the participant diary.

- d. For those participants who are unable to continue participation in the study, but for whom consent is not withdrawn, an early exit visit could be conducted. Participants who wish to withdraw consent from participation in the study could be followed up for safety purposes if desired. This includes safety assessments of the early exit visit (no blood sampling for immunogenicity) and documenting the reason.
- e. Signing of the ICF should be done before any study related activities.
- f. History of SARS CoV 2 vaccination (name/manufacturer of the vaccine and date of administration) \geq 6 months prior to the study will be collected in the SARS CoV 2 Vaccination page in the eCRF.
- g. A full physical examination, including height and body weight, will be carried out at screening. At other clinic visits, a symptom directed physical examination can be performed in case of participant's complaints.

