The study staff can recommend the participant informs their medical care provider. If there are no local country recommendations for COVID-19, the sponsor recommends the participant self-quarantines and does not come for a clinic visit until a negative PCR test could be obtained.

If the participant experiences signs or symptoms of COVID-19 after obtaining a positive SARS-CoV-2 test result, they should contact the study site at the time of symptom onset for

recommendations on actions to follow for further care per local guidance. See section [8.3.1](#) on the reporting periods of this event.

Visit Windows

Visit windows are provided in the [Schedule of Activities](#) in Section [1.3](#). The participant should be encouraged to come on the day planned, but the visit window may be used.

The timings of the post-vaccination visits will be determined relative to the actual day of the corresponding vaccination.

If a vaccination window is missed, efforts will be made to vaccinate the participant as soon as possible, even if out of the window. The timings of the post-vaccination visits will be determined relative to the actual day of the corresponding vaccination, unless they overlap with other scheduled visits, in which case the out of window visit should be documented in the source documents. If the participant refuses to receive the second vaccination, the investigator is encouraged to discuss it with the sponsor.

Screening

Screening may be performed within 28 days prior to the first study vaccination or on the day of vaccination. If screening is performed on the day of vaccination, Visit 1 and Visit 2 will coincide on Day 1. Screening must be completed and all eligibility criteria must be fulfilled prior to randomization and vaccination.

Screening may be conducted in part via a sponsor- and Independent Ethics Committee/Institutional Review Board (IRB/IEC)-pre-approved non-study-specific screening consent process, but only if the relevant pre-screening tests are identical to the per protocol screening tests and are within 4 weeks prior to first vaccination. However, no study-specific procedures, other than these pre-approved pre-screening assessments, will be performed until the participant has signed the study-specific ICF. The -study-specific signed ICF date must be entered into the eCRF.

Sample Collection and Handling

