**Table 2– Visit Windows for Immunogenicity Analysis**

Analysis time point label (relative to Day 1)	Scheduled Visit Number	Visit Type	Window of target day* (Day)
[Day 1]	[2]	Vaccination 1, Immunogenicity and Safety	[N/A]
[Day 29]	[3]	Vaccination 2, Immunogenicity and Safety	[+10/-3]
[Day 57]	[4]	Immunogenicity and Safety	[+10/-3]
[Week 28]	[5]	Immunogenicity and Safety	[+7/-7]

\*Relative to Analysis time point

Time windows may be redefined prior to unblinding if the number of samples excluded as per the definitions above are too numerous.

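### SAP Table 2 counts its exclusion windows from Day 1, the protocol counts Visits 4 and 5 from the actual second vaccination; as written, Table 2 rejects on-schedule Visit 5 samples

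*SAP*

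**What the plan says.** SAP 5.1.1 allocates samples to visits by the planned CRF visit and then applies a timing test: "Visits that are out of the protocol-defined visit windows (see Table 2) will not be included in the per-protocol immunogenicity analysis". The first column of Table 2 is headed "Analysis time point label (relative to Day 1"), and the footnote to the window column reads "Relative to Analysis time point". The windows are -3/+10 days at Day 29 and Day 57, and ±7 days at Week 28. Below the table the SAP adds: "Time windows may be redefined prior to unblinding if the number of samples excluded as per the definitions above are too numerous". Out-of-window visits may also be used in sensitivity analyses.

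The protocol uses a different anchor. The notes to its Schedule of Activities (1.3.1) say that "these visits (including their window) are to be scheduled relative to the actual day of the previous vaccination". The schedule times Visit 4 at 28 days after the second vaccination with -3/+7 days, and Visit 5 at "Post Vac 2 + 180 d" with ±7 days. Section 8 repeats the principle: "The timings of the post-vaccination visits will be determined relative to the actual day of the corresponding vaccination".

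The arms reach the primary S-ELISA time point (28 days after Ad26.COV2.S) at different visits. CoAd is dosed on Day 1, so its sample is Visit 3. Control is dosed at Visit 3, so its sample is Visit 4.

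**The concern.** Two documents give two different tests for whether a sample is in window, and the SAP's test decides who enters the per-protocol immunogenicity analyses. A programmer who follows Table 2 as printed would discard Visit 5 samples taken exactly when the protocol asked for them. At Visit 4 the same programmer would apply to Control a window that does not move with the Control dose, while the CoAd window is fixed to the CoAd dose because that dose defines Day 1. At stake are the exploratory durability results at six months and, to a lesser degree, equal handling of the arms on one primary non-inferiority endpoint. The primary HI samples are Visit 3 in both arms, counted from Day 1, so the anchor conflict does not reach them.

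**Working it through.** **Inputs.** Protocol 1.3.1: second dose on Day 29 -3/+7, so Day 26 to 36; Visit 4 at dose day +28, -3/+7, so +25 to +35; Visit 5 at dose day +180 ±7, so +173 to +187. SAP Table 2: Visit 3 Day 29 -3/+10 = Day 26 to 39; Visit 4 Day 57 -3/+10 = Day 54 to 67; Visit 5 Week 28 = Day 28×7+1 = 197, ±7 = Day 190 to 204.

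**Plan's own figure.** The stated power for one strain is 97.45%. With SD 0.53, margin log10(1.5) = 0.1761, two-sided 5% and a noncentral t, I get 97.3% at 275 per group (305 less the SAP's margin of about 30) and 98.4% at 305. The figure is reproduced closely; nothing below depends on it.

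**Visit 5.**
- Exact 180-day visit: 26+180 = Day 206 to 36+180 = Day 216. The literal window ends on Day 204, so all are rejected. For a second dose on Day 29 the target is Day 209.
- Compliant day pairs: 11 dose days × 15 visit days = 165. Inside Day 190 to 204: dose Day 26 gives 6 (Day 199 to 204), then 5, 4, 3, 2, 1 for Day 27 to 31 and none from Day 32. The sum is 21, so 144 of 165 are rejected.
- The anchor is the second vaccination in both arms, so the loss is the same rule in both.

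**Visit 4, Control primary S-ELISA.**
- Compliant day pairs: 11 × 11 = 121.
- Rejected as early (before Day 54): dose Day 26, 27, 28 give 3+2+1 = 6, drawn 25 to 27 days post-dose.
- Rejected as late (after Day 67): dose Day 33, 34, 35, 36 give 1+2+3+4 = 10, drawn 32 to 35 days post-dose.
- Total 16 of 121; none is an exact 28-day draw. For CoAd, compliant Visit 3 days are Day 26 to 36, all inside Day 26 to 39: 0 of 11 rejected.
- The 105 compliant Control pairs that are kept span 25 to 35 days post-dose; compliant CoAd samples span 26-1 = 25 to 36-1 = 35 days.
- Without requiring Visit 4 to comply with the protocol, Table 2 accepts Control samples from 54-36 = 18 to 67-26 = 41 days post-dose, and CoAd samples from 26-1 = 25 to 39-1 = 38. The Control values 18 to 24 and 36 to 41 all breach the protocol's Visit 4 window. For a second dose on Day 36, a draw on Day 68 (32 days, compliant) is rejected and a draw on Day 54 (18 days, non-compliant) is accepted.

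**Size.** Day pairs are not rates, and the documents give no visit-timing data. As an assumption, let both visits scatter independently around target as discretised normals truncated to -3/+7. Share of compliant Control samples rejected:

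| SD (days) | mean delay 0 | 1 | 2 |
|---|---|---|---|
| 1 | 0.7% | 0.01% | 0.0% |
| 2 | 6.3% | 1.7% | 1.1% |
| 3 | 7.7% | 4.9% | 4.9% |

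The worst case is 0.077 × 275 = 21 samples. S-ELISA power (SD 0.50, noncentral t) is 98.5% at 275/275 and 98.1% at 275/254. If all 121 pairs are equally likely, mean Control sampling time is 30.0 days over all pairs and 29.9 over the 105 kept.

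**The case against.** The best defence is that Table 2 was never meant literally. The exclusion sentence invokes windows defined by the protocol, and the protocol anchors them to the dose. Samples are allocated by planned CRF visit, so Day 57 and Week 28 may be only visit names; the protocol's own schedule prints the same names beside the dose-anchored timing. A rule that throws away every exact 180-day visit is unlikely to have been intended.

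This stands as an account of probable intent. It does not remove the conflict. Table 2 states an anchor, and it is the wrong one. Its +10 shows that it is not a copy of the protocol windows, so a programmer cannot resolve the anchor by assuming that it is. Visit allocation decides which visit a sample belongs to, not whether it is in window.

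The safeguards (redefining windows before unblinding, sensitivity analyses, key tables on the FAS) help, but all are optional. The trigger for redefinition is not quantified, and none of them states the anchor.

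The defence is also right to limit the primary-endpoint claim. A reader might set 18 to 41 days for Control against 25 to 38 for CoAd and infer arm-differential bias in the non-inferiority comparison. The Control extremes need a Visit 4 that already breaches the protocol. Compliant accepted samples have the same span in both arms, and no shift in the GMC ratio has been shown.

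**Conclusion.** The conflict is real and should be corrected in the SAP. Its firmest consequence is at Visit 5: if Table 2 is applied as written, every exact 180-day visit after an in-window second dose is excluded, along with 144 of 165 compliant day pairs overall. This affects both arms and exploratory durability endpoints. The consequence for the primary S-ELISA analysis is an untidy, arm-dependent edge effect: 16 of 121 compliant Control pairs against 0 of 11 CoAd days, or 0% to 7.7% of compliant Control samples under the assumed scatter, with negligible change in power and mean sampling time. If every second dose falls on Day 29, the two arms get the same acceptance interval.

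Two further inferences are not supported. One is that the Control S-ELISA baseline is lost when Visit 3 is late: SAP 5.3.2 defines baseline as the last assessment before vaccination and attaches no window condition. The other is that late second doses will cost many on-time Control samples. The protocol does foresee late doses ("If a vaccination window is missed, efforts will be made to vaccinate the participant as soon as possible, even if out of the window"), and an exact 28-day Visit 4 is rejected once the second dose is on Day 40 or later (40+28 = Day 68). But no frequency is given, and whether such participants stay in the PPSI set depends on a major-deviation list that is not in the documents.

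**What to change.** Restate the target days in Table 2 from actual vaccination dates:

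- Visit 3: 28 days after the actual date of Vaccination 1.
- Visit 4: 28 days after the actual date of Vaccination 2.
- Visit 5: 180 days after the actual date of Vaccination 2, ±7 days.

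For Visits 3 and 4, choose one of two widths. Either use the protocol's -3/+7, which accepts primary S-ELISA samples 25 to 35 days after Ad26.COV2.S in both arms. Or keep -3/+10, which gives 25 to 38 days in both arms, say that it is deliberately wider than the protocol, and delete the description of the windows as protocol-defined. A sentence saying that the Control S-ELISA baseline is the last sample before Vaccination 2, even if Visit 3 is out of window, is optional because 5.3.2 already implies it.

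The cost is a SAP text and programming change before database lock and unblinding, with nothing for sites to do. The downside is that a few late-dosed Control participants stay in PPSI with more time since Day 1 and so more chance of infection. The existing exclusions for N-seroconversion and positive molecular tests limit that.
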